4. PROCEDURES

The proposed study will utilize a prospective, experimental research design. We will recruit adult daily smokers with a history of panic attacks in the last year and they will be randomly assigned to either: (1) Panic and Smoking Reduction Treatment plus d-cycloserine (PSRT+DCS) or Panic and Smoking Reduction Treatment plus placebo (PSRT+PBO). Participants will be adults between the ages of 18-65 who have smoked daily for at least a year, currently smoke an average of at least 8 cigarettes per day, and report a motivation to quit smoking in the next month of at least 5 on a 10-point scale. Moreover, participants will have elevated fears of withdrawal and anxiety related bodily sensations and a tendency to regulate these feelings with smoking, as indexed by meeting or exceeding established cut-off scores on the Smoking Abstinence Expectancies Questionnaire (≥ 78), respectively. Eligible participants will be randomly assigned to either condition by the project biostatistician ([name]. – Consultant at Southern Methodist University). Primary outcome measures will be point prevalence abstinence (PPA), time to first smoking lapse, and time to smoking

relapse. Proposed mediators include panic attacks, distress intolerance, anxiety sensitivity, nicotine withdrawal symptoms, and negative affect. These variables will be assessed at baseline, weekly during the treatment phase, and at 2, 4, 8, 10, 16, and 24 weeks after quit date.

Eligibility Screening

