Internet and Telephone Prescreen & In-person or Telephone Screening. Individuals interested in participating in the study will be directed via various recruitment strategies to an Internet prescreen using REDCap. The first page of the prescreen survey will include the consent form for the prescreen survey, telephone screening, and demographic and medical history questionnaire procedures where participants will be able to give informed consent through REDCap. This online prescreen will assess basic eligibility criteria and individuals who appear potentially eligible will be further assessed via a telephone prescreen. The prescreen procedure is the first point of contact for participants, and it will allow us to ask critical information about the potential participant's willingness and ability to commit to the frequency of clinic visits as well as the assessment of inclusion criteria. Participants will also be asked during the phone screen whether they have sufficient command of the English language, as visits will be conducted in English and all self-report measures are in English. If a participant passes the Internet and Telephone Prescreen, they will complete the Screening assessment either over the phone or asked to come into the lab for an in-person screening. The screening will include a psychiatric evaluation process through the Structured Clinical Interview for DSM-IV (SCID) and the Panic Disorder Severity Scale (PDSS) to evaluate the presence of panic attack history and psychiatric exclusion criteria. The interview will also allow for assessment of primary and secondary diagnoses if applicable. Suicidality will also be assessed at this time using the Columbia-Suicide Severity Rating Scale (C-SSRS). Demographic and general medical health history information will also be captured during the screening assessment. If a participant is assessed over the phone, the demographic and general medical health history survey will be sent to them via REDCap.

In-Person Screening Assessment. If a participant comes into the lab for their screening assessment, they will first read and give signed, informed consent. The researcher will answer any questions they may have and complete the screening. Participants' blood pressure, heart rate, and CO₂ will be measured at this visit.

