5. MEASURES

Assessment Instruments

Screening Measures

Eligibility Screen. This prescreen questionnaire and telephone-screening will assess inclusion and exclusion criteria.

Motivation to Quit Smoking. This 10-item measure will be used to determine participants' pre-cessation motivation to quit smoking (Rundmo et al., 1997).

Demographics. Participants will be asked to provide standard demographic information (i.e. age, gender, race/ethnicity, level of education, etc.) as well as history of medical problems.

Psychiatric History. Diagnostic exclusions and lifetime prevalence of Axis I diagnoses will be determined by the Structured Clinical Interview for DSM-IV (SCID-NP; First et al., 2007) during the screening. The diagnostic interview will be administered by trained research personnel and will be supervised by the PIs. This interview will serve to contextualize participants' psychiatric history at baseline. In addition, the SCID will be conducted at the final follow-up visit (week 29) in order to assess for changes in diagnoses. Anxiety sensitivity interventions have been shown to aid in the prevention of future mental health disorders, so assessing for changes in diagnostic status in this population will be a useful addition to the literature.

Suicide. The Columbia Suicide Severity Rating Scale (C-SSRS; Posner, Oquendo, Gould, et al. 2007) is a standardized measure of current and past self-injurious behavior, suicidal intent, and suicidal behaviors. The C-SSRS has demonstrated good reliability and validity (Hammad et al., 2006; Posner et al., 2007). The C-SSRS will be administered as part of the diagnostic interview in order to assess for a history of suicide attempts or current suicidal thoughts or plans.

Vital Signs. As part of their screening visit, participants' blood pressure will be assessed.

Laboratory Testing. A study physician will review the patient's medical history and conduct a complete physical examination if deemed necessary. Safety evaluations will also include laboratory tests (CBC, chemistry profile, and thyroid function test). A urine pregnancy test will be performed as part of the general physical medical evaluation of patients during the baseline visit and to assess for study exclusion criteria. In addition, a urine pregnancy test will be performed each month following randomization. Blood draws will be performed(if deemed necessary) in our laboratory

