Smoking Cue Appeal Survey (SCAS). The Smoking Cue Appeal Survey (Murray, McHugh, Rowley, Sirota, & [name], 2010) measures cue appeal to sensory smoking cues. An initial study demonstrated good psychometric properties associated with smoking status and craving (Murray et al., 2010).

Barriers to Cessation Scale (BCS). The Barriers to Cessation Scale (Macnee & Talsma, 1995) is a 19-item measure assessing barriers or specific stressors associated with smoking cessation. It has been found to have good internal consistency, good content, and predictive validity (Macnee & Talsma, 1995).

Research Proposal

Smoking Consequences Questionnaire – Brief (SCQ-Brief). The SCQ-Brief is an abbreviated version combining both the Smoking Consequences Questionnaire (SCQ; Brandon & Baker, 1991), an 80-item measure assessing positive and negative smoking outcome expectancies, and the Smoking Consequences Questionnaire - Adult (SCQ-A; Copeland et al., 1995), a 55-item measure considered to be more suitable for adults. The brief version is a 25-item measure that has shown good internal consistency and convergent validity (Rash & Copeland, 2008).

Intolerance for Smoking Abstinence Discomfort (IDQ-Smoking). The IDQ-Smoking questionnaire is a 17-item measure that assesses the intolerance of discomfort associated with recent smoking cessation. The IDQ-S has three reliable components: withdrawal Intolerance, Lack of Cognitive Coping, and Pain Intolerance.

Smoking Status. Self-reports of smoking status will be collected from participants at baseline, weekly throughout treatment and at follow-up assessments. Participant reports of abstinence at all times will be verified by expired carbon monoxide, and additionally at the 8, 10, 16, and 24-week interviews with saliva cotinine (see Table 2). The main outcome analyses are based upon 7-day point prevalence abstinence (i.e., reported abstinence of at least 7 days prior to each scheduled follow-up). Self-report will be overridden by objective verification in the conservative direction (Proceedings of the National Working Conference on Smoking Relapse, 1986).

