In addition to point-prevalence outcomes, we also will use the timeline follow-back (TLFB) procedure for assessing the time to first smoking lapse and the time to first relapse, defined as the 7th day on which smoking occurs. The TLFB procedure has demonstrated good reliability and validity (Sobell & Sobell, 1996). The TLFB will be administered at each follow-up to assess cigarette use since the previous assessment.

Biochemical Verification. Self-reported abstinence at the 8, 10, 16, and 24-week follow-ups will be verified by saliva cotinine (cutoff value of 10 mg/ml) for stated abstinence of 2 weeks or more (cotinine may be incompletely metabolized before this time), and carbon monoxide analysis of breath samples (8ppm cutoff) for stated abstinence of 24 hours to 2 weeks (Jarvis et al., 1987). Saliva samples will be frozen and analyzed by an outside laboratory for cotinine level using radioimmune assay. Expired air carbon monoxide levels will be assessed with a Vitalograph Breathco carbon monoxide monitor (Jarvis et al., 1987). Detected values above the stated cutoff scores will be considered indicative of smoking.

Mood, Emotion, and Cognition

Inventory of Depression and Anxiety Symptoms (IDAS). The IDAS is a 64-item measure assessing specific symptom dimensions of major depression and related anxiety disorders (Watson et al., 2007). The scales are internally consistent and show excellent convergent validity and good discriminant validity (Watson et al., 2007).

Difficulties with Emotion Regulation Scale (DERS). The DERS is a 36-item self-report measure of clinically-relevant difficulties in emotion regulation (Gratz & Roemer, 2004). The scale has been validated in cocaine dependent (Fox et al., 2007) and alcohol dependent (Fox, Hong, & Sinha, 2008) populations.

Research Proposal

NEO Five-Factor Inventory (NEO-FFI). The NEO-FFI is a 60-item self-report measure of five basic personality factors (Costa & McCrae, 1989). The measure has been shown to have high test-retest reliability (Robins et al., 2001) and internal consistency (Costa & McCrae, 1992).

Regulatory Focus Questionnaire (RFQ). The Regulatory Focus Questionnaire (RFQ; Higgins et al., 2001) was derived from a factor analysis of items assessing the history of individuals' success at promotion and prevention tasks over the course of their lives.

Sleep, Financial Strain, Life Stressors

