study for several reasons. First, the study hypotheses are not directly relevant to children or older adults without significant modification to take into account differing cognitive and developmental issues as well as issues related to smoking metabolism. These different issues could manifest in behavior, affect, psychophysiology, and/or neurobiology. If children and older adults were to be included, the study design would, at a minimum, have to take these factors into account and hypotheses would have to be added. To do so, the sample size would have to be increased considerably to yield adequate power to test these additional hypotheses. The budget allocation for an individual project simply does not allow for this possibility without seriously compromising other aspects of the study. Second, we elected not to include individuals below the age of 18 for two significant reasons. One reason is that individuals below the age of 18 experience markedly lower rates of smoking and anxiety-related problems than do adults (Fiore et al., 2000, 2008; Ollendick, Mattis, & King, 1994). Given these findings, it is most parsimonious to sample adults at this stage of treatment development. A second reason is that it has been repeatedly hypothesized that panic problems are rare among children due to their limited cognitive capacities (Nelles & Barlow, 1988; Vasey & Daleiden, 1994). Specifically, youths have a limited ability to attribute anxiety to internal cues or associating the sensations of anxiety with mental or physical catastrophe, a process central to the AS construct. Thus, restricting this initial investigation of AS and smoking to adult participants will help eliminate concerns regarding the cognitive capacities of children. Additionally, if children were to be included, the study design would, at a minimum, have to take these factors into account and additional hypotheses would need to be added. To do so, the sample size would have to be increased considerably to provide for adequate power to test these new hypotheses. Therefore, to focus on individuals below the age of 18 years does not make practical or clinical sense or offer help in developing more generalizable data.

B. INCLUSION/EXCLUSION

Inclusion Criteria:

- Male and female patients ages 18-65 capable of providing informed consent
- Willing and able to provide informed consent, attend all study visits and comply with the protocol
- Daily smoker for at least one year

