- Currently smoke an average of at least 8 cigarettes per day
- Report a motivation to quit smoking in the next month of at least 5 on a 10-point scale
- Evidence of panic attack within the past year and endorsement of smoking as an emotion regulation strategy (i.e., score at least a 78 on the SAEQ).

Exclusion Criteria:

- Subjects who do not use smoking as an emotion regulation strategy
- Current diagnosis of a psychotic, eating, developmental or bipolar disorder
- Significant suicide risk as determined by structured interview
- Pregnant women, lactating women, and women of childbearing potential who are not using medically accepted

Research Proposal

forms of contraception (e.g., IUD, oral contraceptives, barrier devices, condoms and foam, or implanted progesterone rods stabilized for at least 3 months).

- Psychoactive substance abuse or dependence (excluding nicotine dependence) within the past 6 months
- Current use of isoniazid or ethionamide compounds
- A history of significant medical condition and/or be deemed as currently unhealthy by the study physician
- Limited mental competency and the inability to give informed, voluntary, written consent to participate
- Current use of any pharmacotherapy or psychotherapy for smoking cessation not provided by the researchers during the quit attempt
- Concurrent psychotherapy initiated within three months of baseline, or ongoing psychotherapy of any duration directed specifically toward treatment of anxiety or mood disorder other than general supportive therapy initiated at least 3 months prior to the study
- Use of other tobacco products
- Plans to move outside of the immediate area in the next six months
- Insufficient command of the English language

C. BENEFITS

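### Baseline carbon monoxide is measured but not used to confirm smoking at entry, so the CO check on abstinence is weak for anyone already at or below 8 ppm

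*Protocol*

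**What the plan says.** **Entry.** Protocol section 4 describes the participants as adults "who have smoked daily for at least a year, currently smoke an average of at least 8 cigarettes per day". The inclusion criteria in Protocol section 6.B likewise ask for "Daily smoker for at least one year" and "Currently smoke an average of at least 8 cigarettes per day". Section 5 (Eligibility Screen) says how criteria are judged: "This prescreen questionnaire and telephone-screening will assess inclusion and exclusion criteria". The screening assessment itself may be done by telephone. No inclusion or exclusion criterion carries a CO or cotinine threshold.

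**The baseline reading.** Table 2 marks carbon monoxide at baseline. Section 4 describes a breath reading at in-person screening, "Participants' blood pressure, heart rate, and CO₂ will be measured at this visit", and again at the baseline visit of those screened by telephone. Both places print CO₂. The only range and follow-up action given there concern blood pressure.

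**Outcome.** Section 5 (Smoking Status) bases the main outcome analyses on 7-day PPA and states: "Participant reports of abstinence at all times will be verified by expired carbon monoxide". It adds saliva cotinine at weeks 8, 10, 16 and 24, and lets objective results override self-report in the conservative direction. Section 5 (Biochemical Verification) assigns cotinine to stated abstinence of 2 weeks or more, and "carbon monoxide analysis of breath samples (8ppm cutoff) for stated abstinence of 24 hours to 2 weeks". Only values above the cut-off indicate smoking. Table 2 also marks cotinine at post-quit week 4 but has no baseline cotinine.

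**The concern.** A biochemical check on abstinence is informative only if it would have been positive while the person was smoking. The plan takes the reading that could show this and then makes no use of it. If a participant's CO while smoking as usual is at or below 8 ppm, or if the participant does not smoke as claimed, a later reading at or below 8 ppm says nothing about whether behaviour has changed. The rule that objective results override self-report then has little to work with.

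Two things are at stake. The first is the contrast in PPA, one of three primary outcomes: people wrongly counted as abstinent in both arms pull the arms together. The second is the planning value of the abstinence rates. Protocol section 3 says the trial is meant to supply effect-size data for a larger trial, and rates inflated in both arms would carry over into that design.

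**Working it through.** **1. Which claims of abstinence rest on CO alone**

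| Situation | Check specified |
|---|---|
| Quit week and post-quit weeks 1 and 2 | CO only |
| Post-quit week 4 | CO; cotinine in Table 2 but not in the text |
| Weeks 8, 10, 16, 24; stated abstinence of 2 weeks or more | Cotinine |
| Weeks 8, 10, 16, 24; stated abstinence under 2 weeks | CO, on the wording of Biochemical Verification |

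The fourth row matters because the outcome is 7-day abstinence: a claim of 7 to 13 days qualifies as abstinent and falls under the CO rule even at week 24. Someone who was not smoking at entry would be expected to pass cotinine as well, unless the patch raises it.

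**2. The plan's own figures**

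Inputs from the SAP Power Analysis: PPA of 27% (PSRT+PBO) and 43% (PSRT+DCS) at the last follow-up, N = 80, an average of 5 assessments, power .80.

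- Cohen's ω = (0.43 − 0.27) / (2 × √(0.35 × 0.65)) = 0.168, which agrees with the stated .17.
- The .80 cannot be confirmed, because the within-person correlation is not stated. I therefore calibrate to it. A two-sided 5% comparison of two proportions (pooled variance under the null) reaches .80 at 139 per arm. With 5 assessments on 40 people per arm (1:1 assumed), effective n = 200 / (1 + 4 × ICC), so 139 corresponds to an ICC of about 0.11. This is only a scale for reading changes in power.

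**3. Effect of miscounting**

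Let f be the share of entrants whose usual CO is at or below 8 ppm, and g the share of those still smoking who claim abstinence and are not caught. The documents give neither. Assume that both are equal across arms and that true quit rates do not depend on f.

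- Observed PPA = p + (1 − p) × f × g
- Observed difference = 16.0 points × (1 − f × g)

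Example, f = 5% and g = 50%: 0.27 + 0.73 × 0.025 = 0.288 and 0.43 + 0.57 × 0.025 = 0.444, a difference of 15.6 points.

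| f | g | PBO | DCS | Difference (points) | Power at 139 per arm |
|---|---|---|---|---|---|
| 0 | – | 27.0% | 43.0% | 16.0 | 0.80 |
| 5% | 50% | 28.8% | 44.4% | 15.6 | 0.773 |
| 10% | 50% | 30.7% | 45.9% | 15.2 | 0.744 |
| 20% | 50% | 34.3% | 48.7% | 14.4 | 0.685 |
| 5% | 100% | 30.7% | 45.9% | 15.2 | 0.744 |
| 10% | 100% | 34.3% | 48.7% | 14.4 | 0.685 |
| 20% | 100% | 41.6% | 54.4% | 12.8 | 0.570 |

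The rows with g = 100% are the extreme case in which every affected person counts as abstinent throughout; entrants who do not smoke at all would behave this way.

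**4. In people.** Of 80 participants, 5% is 4 and 10% is 8. At g = 50% and 40 per arm, the expected number wrongly counted abstinent is 40 × 0.73 × 0.025 = 0.73 (PBO) and 40 × 0.57 × 0.025 = 0.57 (DCS) for f = 5%, and twice that, 1.46 and 1.14, for f = 10%.

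**The case against.** The case on the other side is substantial, and most of it stands as a limit on size.

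- **Later readings still count.** A reader might infer that CO can never contradict these participants. One low baseline reading does not show that. CO is repeated, it can vary between visits, and any later value above 8 ppm overrides self-report. A low reading also does not create abstinence: the participant must report 7 smoke-free days.
- **Cotinine applies where the power figures sit.** The 27% and 43% refer to the last follow-up, where cotinine is the specified check for claims of 2 weeks or more. The dilution computed above is therefore an upper bound there. Nicotine from the patch, whose total duration is not stated, could raise cotinine, but under the override rule that would code a person as smoking, not abstinent.
- **No incentive to claim abstinence.** A reader might point to the payments of up to $200. Protocol section 8 says they do not depend on smoking status.
- **Scope.** Lapse and relapse times come from the timeline follow-back, so the dilution concerns PPA. The SAP itself says the trial is not powered for small differences.
- **Timing and side effects.** The SAP is dated June 2017, and the Protocol expected data collection to end in August 2017, so a new entry rule may reach few or no participants. A CO floor also depends on time since the last cigarette and could turn away genuine smokers near 8 per day.

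What does not fall is the core: the reading is scheduled, the cut-off is the protocol's own, and nothing connects them at entry. Cotinine leaves the early visits, claims of under 2 weeks and people not smoking at entry uncovered.

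**Conclusion.** The point holds as a modest weakness in verification. Smoking at entry rests on self-report, baseline CO governs nothing, and for participants at or below 8 ppm at entry the CO check cannot reliably refute a claim of abstinence. The main exposure is at the early post-quit visits and for stated abstinence of under 2 weeks.

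If 5% to 10% were affected and half of those still smoking were miscounted, the difference would shrink from 16.0 to about 15.6 to 15.2 points, with power falling from .80 to about .77 to .74 on the calibrated scale. Where cotinine also applies, these are upper bounds. They rest on assumed values of f and g, on equality of both across arms, and on an approximation to the SAP's simulation.

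Two stronger readings are not supported. The first is bias in favour of one arm: the entry rule is common to both arms and allocation is random and blinded, so inflated rates and a diluted contrast are what to expect. The second is a serious loss of power, such as the 0.570 in the table. That needs 16 of 80 participants affected and every one of them counted as abstinent throughout, and the documents offer no evidence for either.

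**What to change.** 1. **Sensitivity analysis (SAP, Data Analysis).** Flag participants whose baseline CO is at or below 8 ppm, report their number by arm, and pre-specify a repeat of the PPA analysis without them. Name which reading counts, since section 4 places it at screening for some participants and at the baseline visit for others. Either reading precedes the first DCS or placebo administration in week 3, so the exclusion cannot depend on treatment and the arms stay comparable. The count also replaces the assumed f with a known number of low readers. Cost: one extra model run and a slightly smaller n.
2. **Entry rule, only if enrolment is still open (Protocol sections 4 and 6.B).** Require a baseline CO above 8 ppm before randomisation, with one repeat reading allowed. Cost: one eligibility line; a few genuine light smokers will need a repeat or will not be enrolled.
3. **Wording (Protocol section 4, screening and baseline visits).** Replace CO₂ with carbon monoxide so that the text agrees with Table 2. No cost beyond the edit.
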